7.1.1.2.2. Monitoring of Vital Signs

Vital signs monitoring will occur at every visit. Seated/reclined blood pressure (BP) will be recorded before each dialysis session, approximately every 30 minutes during dialysis, and at the end of the session. Other vital signs will be captured at the beginning and end of each visit; these include heart rate (beats per minute [bpm]), respiratory rate (breaths per minute), and body temperature. Vital signs will be measured after the subject has been seated/reclined for ~5 minutes.

Subjects will be monitored for IDH (see Definitions). Beginning at run-in, should the number of occurrences of IDH exceed a predetermined threshold based on the subject's Expected IDH Rate, then the subject will be discontinued or de-escalated to a previously tolerated, smaller column size at blood-flow rates up to 450 mL/min (Appendix 17.1).

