4.7.2 IDH Events

The number and percentage of subjects will be summarized for the Safety, Evaluable and PP populations, by column size and blood-flow rates combination, for the following:

- Historical IDH Rate (0,1,2,3,4)
- Number of IDH Events (0, 1, 2, 3, 4, 5, 6)
- Change in IDH Rate above the Historical IDH Rate (0, 1, 2, 3)

A listing of IDH Rate, including each subject's historical IDH rate and number of hypotensive events, will be provided.

Protocol Defined IDH Definitions:

Statistical Analysis Plan AKST1210-101

Rev. A Page 16 of 28

Intradialytic hypotension/hypotensive event (IDH)

A systolic blood pressure (SBP) < 90 mmHg that occurs during hemodialysis and is confirmed by repeat measurement.

Expected IDH Rate

The expected number of occurrences of IDH per weekly treatment period derived from a subject's Historical IDH rate (see section below and Protocol Appendix 17.1). The expected IDH Rate is compared

with the actual IDH rate and used to assess escalation, de-escalation, and discontinuation.

Historical IDH Rate

The number of occurrences of IDH as documented in a subject's medical record during a recent 8-week period prior to the run-in period. Subjects with 7 or more IDH events during this 8-week interval will be excluded.

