4.9.3 Vital Signs

Vital signs, including blood pressure (mmHg), heart rate (beats/min), respiratory rate (breaths/min), and body temperature (C), will be summarized. Seated/reclined BP will be recorded before each dialysis session, every 30 minutes during dialysis, and at the end of the session. Other vital signs will be captured at the beginning and end of each visit. If screening and/or EOS occur on a day in which a subject is not receiving HD, vital signs will be measured after the subject has been seated/reclined for ~5 minutes. Observed values will be tabulated at baseline, and at each scheduled post-baseline time point. Change from baseline at each scheduled post-baseline time point will also be summarized. Change from baseline in blood pressure will also be presented in figures.

Additionally, a 'Repeated SBP < 90 mmHg or action taken to HD' listing will be populated if there are two SBP < 90 within 30 minutes of the start of the HD, or if in the HD data we have additional saline use entered as 'Hypotension', or there is a log record in the HD data within 30 minutes of a < 90 SBP with a change in bloodflow rate, dialysate flow rate, or ultrafiltration rate (this would include if the HD was stopped).

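### The repeated-SBP trigger in the SAP 4.9.3 listing covers only the first 30 minutes of HD, so a later confirmed IDH with no saline entry or setting change would not be listed

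*SAP*

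**What the plan says.** SAP 4.7.2 defines an IDH event as "A systolic blood pressure (SBP) < 90 mmHg that occurs during hemodialysis and is confirmed by repeat measurement". The definition sets no time limit within the session and does not require any intervention. The protocol's List of Definitions agrees.

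SAP 4.9.3 adds a listing whose title covers repeated SBP below 90 mmHg or action taken on the HD. A session enters it under any one of three conditions joined by 'or':

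1. Repeated readings: "two SBP < 90 within 30 minutes of the start of the HD".
2. Saline: "or if in the HD data we have additional saline use entered as 'Hypotension". No time limit is given.
3. Setting change: "there is a log record in the HD data within 30 minutes of a < 90 SBP with a change in bloodflow rate", or in the dialysate-flow or ultrafiltration rate, including a stopped session. The 30 minutes here run from the low reading, so the condition can apply at any point in the session.

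Pressure is taken before HD, then "approximately every 30 minutes during dialysis, and at the end of the session" (Protocol 7.1.1.2.2; SAP 4.9.3 gives the same schedule).

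**The concern.** The first trigger is the only one of the three that rests on repeated low readings alone, which is how an IDH event is defined. Taken literally, it anchors the 30 minutes to the start of the session instead of to the other low reading. Two low readings in the second or third hour then do not meet it.

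The protocol summary names IDH as the most important known potential risk of the column, and the number of IDH events is part of the primary endpoint. SAP 4.7.2 tabulates those events but gives no rule for deriving them from the pressure data. Protocol 17.1.3 has IDH recorded as AEs, and SAP 4.7.1 summarizes TEAEs as entered in the database. The 4.9.3 listing is therefore the only SAP rule that flags repeated low SBP from the readings themselves. At stake is its use as a cross-check on the recorded IDH events.

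**Working it through.** The plan states no figure for this listing, so there is none to reproduce. The check compares the trigger logic with the definition and works out how much of a session the first trigger covers.

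**Inputs**
- Trigger 1 window: 30 minutes from the start of HD (SAP 4.9.3).
- Session length: about 4–6 h at 250 mL/min and 3–4 h at up to 450 mL/min (SAP 3.1; Protocol 4.1).
- Scheduled pressure readings: before HD, every 30 minutes, and at the end (SAP 4.9.3; Protocol 7.1.1.2.2).

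**Session time inside the window** = 30 / (60 × hours); **scheduled readings during HD, end reading included** = 60 × hours / 30.

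| Session | Time inside window | Time outside | Readings during HD | Of these, in first 30 min |
|---|---|---|---|---|
| 3 h | 30/180 = 16.7% | 83.3% | 6 | 1 |
| 4 h | 30/240 = 12.5% | 87.5% | 8 | 1 |
| 6 h | 30/360 = 8.3% | 91.7% | 12 | 1 |

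Only one scheduled reading taken during HD falls in the window. Two low readings during HD inside it therefore need an unscheduled repeat. If the pre-HD reading is also counted, the window holds 2 of 7 readings (3 h) or 2 of 13 (6 h), but a pre-HD reading is not intradialytic under the definition.

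**Path of a confirmed IDH through the three triggers**

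| Case | Trigger 1 | Trigger 2 | Trigger 3 | Listed? |
|---|---|---|---|---|
| Both low readings in first 30 min | met | – | – | yes |
| Later, saline entered as 'Hypotension' | not met | met | – | yes |
| Later, setting changed within 30 min of a low SBP | not met | – | met | yes |
| Later, neither action logged | not met | not met | not met | **no** |

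The gap is the last row. It is not an artificial case. The protocol summary includes supine positioning and lower-limb elevation among its IDH mitigations, and neither would meet trigger 2 or 3. The documents give no rate of IDH without saline or a setting change, so the frequency of that row cannot be calculated.

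**The case against.** The strongest reply is that the listing is one supplementary output under Other Safety Analyses and that IDH is captured elsewhere. SAP 4.7.2 has its own IDH listing, all IDH after consent is recorded as AEs and all AEs are listed, and SAP 4.1 says listings in general contain all data collected. The pressure readings should therefore be available for inspection. The phrase may also be a slip for two readings within 30 minutes of each other, and the listing shells, which are separate files, might show this.

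Most of that stands, and it rules out several stronger readings:

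- *All later IDH is missed.* This would follow if the first trigger stood alone. Triggers 2 and 3 are joined by 'or' and are not tied to the session start.
- *This is the only data-based check on IDH.* The readings themselves are due to be listed. What is unique to 4.9.3 is an automatic flag; otherwise a reader must find the pairs by eye.
- *The trigger will almost never fire.* The IDH definition requires a repeat measurement, so unscheduled readings are expected. The withdrawal rule in Protocol 5.4.1 applies only to a confirmed low SBP before HD, so an unconfirmed low reading at the start followed by a low 30-minute reading could still fire it.
- *The primary count or escalation decisions would be wrong.* Neither the 4.7.2 counts nor the Appendix 17.1 decisions are said to use this listing.
- *83–92% of IDH events are lost.* That range is session time outside one trigger's window. It is not a share of events.

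The reply does not remove the mismatch. The SAP defines the event one way and flags it another, and nothing in the text marks the difference as intended.

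**Conclusion.** The point holds as a limited, correctable error in a stated rule. Followed literally, the repeated-SBP trigger covers about 8–17% of a 3–6 hour session, while the IDH definition covers all of it. A confirmed IDH after the first 30 minutes, with no saline entered as 'Hypotension' and no logged setting change within 30 minutes of a low SBP, would not enter the listing. How many events this concerns is unknown.

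This rests on three assumptions: that the phrase is programmed as written, that pressure is measured on the stated schedule, and that sessions run within the planned lengths. If the shells already use the interval between readings, only the SAP wording is at fault. No primary estimate is shown to change. The reason to correct it is that the flag concerns the trial's main named risk and should match the SAP's own definition.

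**What to change.** In SAP 4.9.3, replace the first trigger with: *two SBP < 90 mmHg readings within 30 minutes of each other (or at consecutive readings) at any time from the start to the end of HD*. The consecutive-readings clause matters because the protocol's interval is approximate, and a strict 30-minute limit would drop pairs taken slightly further apart. Leave triggers 2 and 3 unchanged.

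Add a sentence that the listing will be reconciled against the IDH events counted in SAP 4.7.2, with unmatched sessions queried and the outcome documented. Check the listing shell for the same wording.

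The cost is one SAP phrase, one line of programming and a small reconciliation step. No additional data are needed, and no clinical rule is affected.

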4.9.4 Pregnancy tests

Pregnancy test results will be provided for women of childbearing potential (WOBCP) in a listing only.

4.9.5 Laboratory Data

Analyses on hematology, chemistry, coagulation, and other clinical lab tests will consist of the followings:

- Observed values at baseline and each scheduled post-baseline time point, along with change from baseline at each scheduled post-baseline time point
- Number and percentage of subjects with abnormal laboratory tests indicating serious condition at each scheduled time point

Hematology: complete blood count (CBC), haptoglobin (Hp), Hgb, plasma-free Hgb.

Chemistry: Alanine aminotransferase (ALT), albumin, aspartate transaminase (AST), bicarbonate (HCO₃), bilirubin (total), blood urea nitrogen (BUN), calcium (Total), chloride (Cl), creatine kinase (CK), creatinine, glucose, hemoglobin A1c (HbA1c), lactate dehydrogenase (LDH), magnesium (Mg), potassium (K), phosphate, protein (total), sodium (Na).

Coagulation: Activated partial thromboplastin time (aPTT), prothrombin time/international normalized ratio (PT/INR).

Other: Complement C3 and C4, gastrin, Heparin Anti-Xa (only for patients on low molecular weight heparin), osteocalcin, parathyroid hormone (PTH), thyroid-stimulating hormone (TSH).

Please refer to Protocol Section 15.3 Schedule of Laboratory Tests for scheduled time points of each test.

The tests will be presented in the standardized units. Any data contains '>' or "<" sign will be converted to numeric for the summary tables. If the standardized value contains the "<" sign, the data used for the summary tables will be derived by extracting the numeric value from the standardized value and subtracting $0.1^{(N+1)}$ to that numeric value, where N is the number of decimals in the numeric value. For example, if the standardized value = "< 0.3", it will be converted to 0.29 for summary statistics in the table. If the original value contains the ">" sign, the data used for the summary tables will be derived by extracting the numeric value from the standardized value and adding $0.1^{(N+1)}$ to that numeric value, where N is the number of decimals in the numeric value. For example, if the standardized value =">1000", it will be converted to "1000.1". Subject listings will present all data collected (the '>' and '<' signs will be kept) along with toxicity grading.

Results for hematology, chemistry, coagulation, and other clinical lab tests will be provided in separate listings. A listing of abnormal laboratory tests indicating serious condition will also be provided.

Labs that can indicate serious condition if outside reference range:

Analyte	Sex	MAX YEARS	Units	Critical Low	Critical High
Chemistry					
Albumin	M/F	60	g/dL	2.5	
	M/F	90	g/dL	2.5	
	M/F	150	g/dL	2.5	
ALT	Male	150	IU/L		190
	Female	150	IU/L		160
AST	M/F	150	IU/L		120
Bilirubin Total	M/F	60	mg/dL		5.0
	M/F	90	mg/dL		5.0
	M/F	150	mg/dL		5.0

Statistical Analysis Plan AKST1210-101

Bicarbonate (CO2 or HCO3)	M/F	150	mmol/L	9	
Calcium	M/F	60	mg/dL	6.9	12.1
	M/F	90	mg/dL	6.9	12.1
	M/F	150	mg/dL	6.9	12.1
Glucose Fasting	M/F	150	mg/dL	39	401
Glucose Random	M/F	150	mg/dL	39	401
Magnesium	M/F	59	mg/dL	0.9	7.1
	M/F	90	mg/dL	0.9	7.1
	M/F	150	mg/dL	0.9	7.1
Phosphorus	M/F	150	mg/dL	1.4	
(phosphate)					
Potassium	M/F	150	mmol/L	2.7	6.1
Sodium	M/F	90	mmol/L	119	156
	M/F	150	mmol/L	119	156
Total Protein	M/F	150	g/dL		10.1
Hematology					
WBC	M/F	150	K/uL	1.4	25.1
Hemoglobin	Male	150	g/dL	8.0	20.1
	Female	150	g/dL	8.0	20.1
Hematocrit	Male	150	%	25.0	60.1
	Female	150	%	25.0	60.1
Platelet	M/F	150	K/uL	50	1001
Abs Neutrophil	M/F	150	K/uL	1.0	

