Baseline is the first value after the start of HD with the column. For the assessments that do not take place during the treatment weeks (e.g., ECG, physical examination, etc.), the value from Screening will be the baseline. Baseline for lab values will be the last non-missing value prior to the start of HD with the column.

Change from baseline is the post-treatment value minus baseline value.

Subjects who de-escalate (i.e., do not proceed to the next column size and blood-flow rate combination) will only be included in analysis up to the point of de-escalation.

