4.7.3 Change in Total and Free Hemoglobin

Plasma levels of total Hgb and free Hgb at baseline (i.e., the last nonmissing value prior to the start of HD with the column) and each scheduled post-baseline timepoint, along with change from baseline at each scheduled post-baseline timepoint will be summarized for the Safety, Evaluable and PP populations, by each column size and blood-flow rate combination and total.

A listing of total and free Hgb level, as well as the changes from baseline at each scheduled post-baseline timepoint will be provided.

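### If results are reported as '<L', the SAP's substitution pulls the tabulated plasma-free Hgb rise and haptoglobin fall towards no change by up to one reporting limit, and the abnormal-laboratory count has no limit for either marker

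*SAP*

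**What the plan says.** - **Substitution.** SAP 4.9.5 states that, for a standardized value with a '<' sign, the summary-table figure "will be derived by extracting the numeric value from the standardized value and subtracting" 0.1^(N+1), where N is the number of decimals. In its own example, '< 0.3', "it will be converted to 0.29 for summary statistics in the table".
- **Scope.** The hematology set in the same section is "complete blood count (CBC), haptoglobin (Hp), Hgb, plasma-free Hgb". For listings the signs are kept and a toxicity grade is added: "Subject listings will present all data collected".
- **Endpoint.** SAP 4.7.3 summarizes "Plasma levels of total Hgb and free Hgb at baseline" and at each later time point, with change from baseline. SAP 2.3 makes change in free Hgb a component of the primary endpoint.
- **Baseline.** SAP 4.1: "Baseline for lab values will be the last non-missing value prior to the start of HD with the column". In Protocol 15.3 the only pre-column visit with plasma-free Hgb or haptoglobin is V4.
- **Abnormal count.** SAP 4.9.5 plans "Number and percentage of subjects with abnormal laboratory tests indicating serious condition at each scheduled time point". The limits come from the table headed "Labs that can indicate serious condition if outside reference range". Its hematology rows are WBC, hemoglobin, hematocrit, platelets and neutrophils. It has no row for plasma-free Hgb, haptoglobin or LDH.

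**The concern.** A result of '<L' may be anything from 0 up to L, and the rule takes the top of that range. For the two hemolysis markers this matters in one direction. Hemolysis raises free Hgb, so a low value at V4 is the one that could be censored, and placing it at about L makes the computed rise as small as possible. Hemolysis lowers haptoglobin, so the on-column value is the one that could be censored, and placing it at about L makes the computed fall as small as possible. Both errors point towards no change.

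The planned count of abnormal values could have served as a check that does not depend on the substituted number, but it has no limit for either marker. With about 12 evaluable subjects and few sampling visits, a tabulated change near zero in a primary component could reflect either the blood or the substitution. The summary tables as planned would not tell the reader which.

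**Working it through.** **1. Reproduce the SAP's figures.** '< 0.3' has N = 1: 0.3 − 0.1² = 0.29. '>1000' has N = 0: 1000 + 0.1 = 1000.1. Both match SAP 4.9.5.

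**2. Inputs for the bias.** The documents state no reporting limit for either assay. Assume L = 10 units with no decimals, so '<10' is tabulated as 9.9; results can be read as multiples of L. SAP 4.7.3 has no rule of its own for '<' values, so the 4.9.5 rule is taken to apply there.

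**3. Bounds when one value is censored.**
- Free Hgb, V4 censored: tabulated rise = post − 9.9; true rise is at most post.
- Haptoglobin, on-column value censored: tabulated fall = baseline − 9.9; true fall is at most baseline.

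| Quantified value | Tabulated change | Largest true change | Least share shown |
|---|---|---|---|
| free Hgb 11 | 1.1 | 11 | 10% |
| haptoglobin 12 | 2.1 | 12 | 18% |
| either 20 | 10.1 | 20 | 50% |
| either 50 | 40.1 | 50 | 80% |
| either 100 | 90.1 | 100 | 90% |

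The shortfall is at most 9.9, that is, no more than one reporting limit, whatever the size of the change. If both values are '<10', the tabulated change is 9.9 − 9.9 = 0, and a true rise of just under 10 is not seen.

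**4. Effect on a group mean.** Simulation of 200,000 subjects under assumed distributions: lognormal baseline with log SD 0.6, and a post/baseline ratio with log SD 0.3.

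| Scenario | Relevant value censored | True mean change | SAP mean change | Lost |
|---|---|---|---|---|
| Free Hgb doubles, median baseline 0.3L | 98% | 3.90 | 1.20 | 2.70 (69%) |
| same, 0.6L | 80% | 7.86 | 5.50 | 2.36 (30%) |
| same, 1.0L | 50% | 13.12 | 11.85 | 1.27 (10%) |
| same, 2.0L | 12% | 26.18 | 25.94 | 0.24 (1%) |
| Haptoglobin falls 90%, median baseline 1.5L | 100% | −16.08 | −8.71 | 7.37 (46%) |
| same, 3L | 96% | −32.18 | −25.97 | 6.21 (19%) |
| same, 10L | 50% | −107.29 | −105.49 | 1.80 (2%) |

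In the first row 78% of subjects show a change of exactly 0, and the SAP median rise is 0 against a true median of 2.9. The loss therefore runs from about two thirds of the mean change to almost nothing, depending on where the values lie relative to L.

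**5. Where counts can be filled.** As far as the table in Protocol 15.3 can be read, haptoglobin and plasma-free Hgb are scheduled at V4, V6, V9, V18 and V21. These are the run-in, S-15 at both flow rates and S-35 at both flow rates. Neither marker is scheduled in the S-25 weeks.

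**The case against.** A reader might infer that hemolysis on the column could be hidden by this plan. The documents do not support that, for these reasons:

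- **The bias is conditional.** The rule is generic to all laboratory tests. Nothing in the documents shows that free Hgb or haptoglobin will in fact be reported as '<'.
- **It is bounded.** A change of several reporting limits still shows, as the lower rows of the first table make clear.
- **Other outputs remain.** Observed levels are tabulated with minimum and maximum, and a quantified on-column free Hgb maximum is untouched by the rule. Listings keep the signs, and free Hgb changes are listed. Total Hgb is summarized and, with hematocrit, has critical limits. De-escalations for anemia are counted. Protocol 7.2 makes clinically significant laboratory values AEs, and these are tabulated.
- **The flow-rate contrast is largely safe.** Within a subject, one censored V4 value cancels when the changes at the two flow rates are compared. Only censored on-column values affect that contrast.
- **Part of the loss lies in the assay.** If both values are below L, setting '<' to 0 also gives a change of 0.

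All of this stands, and it limits the point to attenuation in the summary tables and a gap in the count. It does not remove the point. Listings give no count by combination, and the SAP names no grading scale. The AE route depends on an investigator's judgement. Total Hgb is not specific to hemolysis. Total bilirubin has a limit but is scheduled only at screening and V12, and LDH only at screening. Protocol 10.4.3 allows shift tables against the reference range as an option, but SAP 4.9.5 does not take them up.

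**Conclusion.** The point holds in a limited form. Where a V4 free Hgb or an on-column haptoglobin is reported as '<L', the tabulated rise or fall is attenuated towards no change by up to one reporting limit. That is a large share of a change close to the limit and a small share of a change of several limits. This assumes that some results are censored and that the 4.9.5 rule also feeds the 4.7.3 tables. If nothing is censored there is no bias. Independently of that assumption, the abnormal-laboratory count cannot register either hemolysis marker, although change in one of them is part of the primary endpoint. The other outputs give partial information, so this is an inexpensive improvement to the tables. It is not evidence that a hemolysis signal would be missed.

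**What to change.** In SAP 4.7.3 and 4.9.5:

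1. Report n (%) of subjects with post-HD plasma-free Hgb above the central laboratory's upper reference limit, and with haptoglobin below its lower reference limit. Give these at V4 as the no-column reference and for S-15 and S-35 at both flow rates. State that the S-25 weeks have no scheduled data. These counts do not depend on the substituted number as long as L does not exceed the reference limit concerned.
2. State the reporting limit of each assay and the number of '<' results at each time point.
3. Repeat the free Hgb and haptoglobin change summaries once with '<' values set to 0, as the opposite bound. For example, a V4 result of '<10' followed by 20 gives 10.1 under the SAP rule and 20 under this one; the true rise lies between about 10 and 20. Note that changes with both values below L stay unquantifiable under either rule.

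The cost is one extra table and a repeated summary from samples already scheduled. The free Hgb result may look slightly less favourable.
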